4.6.2.1 Permitted, Restricted, and Prohibited Medications

Prohibitions and restrictions for concomitant medications should be followed between the initial screening visit and Visit 7/EOT/ET as specified in [Appendix A](#) and [Appendix B](#). These appendices do not constitute an exhaustive list and any questions regarding prohibited and restricted medications should be discussed with the Medical Monitor or designee.

Use of medications that could interfere with study conduct or any questions regarding prohibited and restricted concomitant medications should be reviewed and/or discussed with the Medical Monitor or designee.

Medications that can prolong QT interval are prohibited (or restricted if approved by the Medical Monitor) as specified in [Appendix A](#).

Permitted concomitant medications should remain at a stable dose throughout the study.

If a subject is on a medication restricted by the protocol, the medication should be adjusted if it is determined by the Investigator to be clinically appropriate (e.g., if the subject's symptoms are not well-controlled or if the subject cannot tolerate the current medication) in consultation with the treating physician.

Subjects who require current treatment with a prohibited medication will be withdrawn from the study.

Subjects who have taken a prohibited medication during the study will be withdrawn from the study unless:

- the prohibited medication has been discontinued, AND
- withdrawal from the study presents an unacceptable medical risk to the subject

The justification to allow the subject who has taken a prohibited medication to continue in the trial will be made by the Sponsor/Medical Monitor, with medical input from the Investigator, and will be documented. If a subject is allowed to remain in the trial, this will be reported as a major protocol deviation and not a waiver.

5 INVESTIGATIONAL PRODUCT

5.1 Investigational Product Description

The investigational product will be pimavanserin 34 mg (provided as 1×34 mg capsule). Capsules will be administered orally as a single dose once daily.

5.1.1 Formulation, Appearance, Packaging, and Labeling

The Sponsor will supply pimavanserin 34 mg capsules.

Commercial pimavanserin 34 mg capsules are opaque white and light green capsules with “PIMA” and “34” printed in black. Each pimavanserin capsule contains 40 mg of pimavanserin tartrate, which is equivalent to 34 mg of pimavanserin free base. [REDACTED]

[REDACTED]

[REDACTED]

Pimavanserin is manufactured under current Good Manufacturing Practices.

During the treatment period, study drug will be distributed in a quantity sufficient to ensure the subject has an adequate supply of study drug between study visits.

5.1.2 Product Storage and Stability

Investigational product must be stored between 20°C and 25°C (68°F and 77°F) in a secure area with restricted access and according to local and national regulations. Excursions are permitted between 15°C and 30°C (59°F and 86°F) [See USP Controlled Room Temperature].

5.1.3 Dosing and Administration

Study drug will be dispensed to the subject to take home. Each daily dose consists of one capsule to be taken orally, once daily. The capsules may be taken with or without food. The first dose should be taken on the morning of the day after the Baseline visit.

5.1.4 Method of Assigning Subjects to Treatment Groups

All subjects will be in the 34 mg pimavanserin treatment group.

5.1.5 Blinding

This is an open-label study.

5.1.6 Study Drug Compliance

If a subject misses one dose of study drug, he or she should not take an extra dose the next day.

If a subject shows significant undercompliance (<80% compliance) between any two scheduled visits, the Medical Monitor should be notified to determine if the subject remains eligible for the study and whether the incident should be considered a protocol deviation.

In the event that a subject is permanently unable to return study drug to the site (i.e., drug is lost, destroyed, or discarded), the subject/caregiver testimony is to be used in determining compliance.

5.1.7 Overdose

An overdose is a deliberate or inadvertent administration of a treatment at a dose higher than the maximum recommended dose per protocol. It must be reported, irrespective of outcome, even if toxic effects were not observed ([Section 7.4.4](#)). All events of overdose are to be captured as protocol deviations.

5.2 Investigational Product Accountability Procedures

The Investigator or designee will keep current and accurate records of the study drug product dispensed, used, and returned for each subject to assure the regulatory authority and the Sponsor that the study drug is being handled appropriately. Subjects should be instructed to return all packaging and unused study drug to the Investigator at regularly scheduled clinic

visits and ET visits. Any study drug supplied is for use in this study only and should not be used for any other purpose.

At appropriate intervals during the study, study drug reconciliation will be performed by the Sponsor (or designee) who may return appropriate unused study drug and used and unused packaging to the Sponsor's designee for destruction.

At the conclusion of the study, final study drug reconciliation will be conducted at the site. Final study drug accountability documentation will be maintained at both the site and at the Sponsor. Any remaining unused study drug and all used and unused packaging will be sent back to the Sponsor's designee for destruction.

6 STUDY PROCEDURES

Study specific procedures are detailed below. All assessments will be completed according to the schedule described in [Table S-1](#). Every effort should be made to complete the required procedures and evaluations at the designated visits and times.

All references to performing assessments, procedures, and evaluations at the clinic, both in [Table S-1](#) and in other parts of this protocol, should be understood as including the option of performing these at the subject's home in the presence of a member of the clinical site staff and the subject's caregiver.

6.1 Screening Assessments

6.1.1 Mini-Mental State Examination

The MMSE is a brief 30-point questionnaire that is used to quantitatively assess cognition ([Folstein et al. 1975](#)). The MMSE includes simple questions and problems in a number of areas: the time and place of testing, repeating lists of words, arithmetic, language use and comprehension, and copying a drawing. Only subtraction of serial 7s will be used in this study; spelling the word 'world' backwards option should not be used. The MMSE is being used in this study to screen for cognitive impairment.

6.1.2 Neuropsychiatric Inventory

The NPI was developed to assess psychopathology in dementia patients ([Cummings et al. 1994](#)). The original NPI evaluated 10 neuropsychiatric disturbances common in dementia: delusions, hallucinations, agitation, dysphoria, anxiety, apathy, irritability, euphoria, disinhibition, and aberrant motor behavior. Two other domains, nighttime behavior disturbances and appetite and eating abnormalities, were subsequently added to the NPI ([Cummings 1997](#)).

At Screening (Visit 1) and Baseline (Visit 2), the degree of the patient's neuropsychiatric symptoms will be evaluated using two of the domains of the Neuropsychiatric Inventory (NPI), Domain A (Delusions) and Domain B (Hallucinations).

6.2 Efficacy Assessments

All scales should be conducted in the “on” state.

6.2.1 Functional Status Questionnaire

The Functional Status Questionnaire is a self-administered questionnaire that provides an assessment in ambulatory patients of physical, psychological, social, and role function ([Jette et al. 1986](#)). It comprises 34 core items that produce 6 summary scale scores:

- Basic activities of daily living (eating, dressing, bathing, moving in and out of bed or chair, walking indoors e.g., in the home)
- Intermediate activities of daily living (walking several blocks; walking one block or climbing one flight of stairs; house cleaning, yard work, or home maintenance; doing errands e.g., grocery shopping; driving a car or using public transportation; doing vigorous activities e.g., running, lifting heavy objects, participating in strenuous sports)
- Psychological function and mental health (been a very nervous person; felt calm and peaceful; felt downhearted and blue; been a happy person; felt so down in the dumps that nothing could cheer you up)
- Social/role function
 - Work performance (done as much work as others in similar jobs, worked for short periods or taking frequent rests because of your health, worked your regular number of hours, done your job as carefully and accurately as others with similar jobs, worked at your usual job but with some changes because of your health, feared losing your job because of your health)
 - Social activity (had difficulty visiting with relatives and friends, had difficulty participating in community activities [e.g., religious services, social activities, volunteer work], had difficulty taking care of other people [e.g., family members])
 - Quality of interaction (isolated yourself from people around you, acted affectionate toward others, acted irritable toward those around you, made unreasonable demands on family and friends, gotten along well with other people).

It also includes 6 single-item scores (work situation; days per month in bed due to illness or injury; days per month when illness injury reduced activities normally performed for half a day or more; satisfaction with sexual relationships; satisfaction with own health; frequency of social interaction).

6.2.2 Schwab and England Activities of Daily Living Scale (Caregiver and Patient Version)

The Schwab & England ADL Scale is widely used in PD. It is rated by physicians, patients, or staff using a 0% to 100% scale with 10% intervals, where 100% is “Completely independent. Unaware of difficulty” and 0% is “Vegetative functions...Bedridden” ([Schwab and England 1969; McRae et al. 2000](#)).

6.2.3 Movement Disorders Society – Unified Parkinson’s Disease Rating Scale Parts I and II (Caregiver and Patient Version)

The MDS-UPDRS is a comprehensive battery of motor and behavioral indices derived from the Columbia Scale ([Fahn et al. 1987](#)). The MDS-UPDRS Parts I and II will be used to assess Non-Motor Aspects of Experiences in Daily Living (nM-EDL) (Part I) and Motor Aspects of Experience of Daily Living (M-EDL) (Part II) and consist of 13 items each ([Goetz et al. 2008](#)).

Part I has two components: Part IA concerns a number of behaviors that are assessed by the Investigator with all pertinent information from patients and caregivers, and Part IB is completed by the patient with or without the aid of the caregiver, but independently of the Investigator. These sections can, however, be reviewed by the rater to ensure that all questions are answered clearly, and the rater can help explain any perceived ambiguities. Part II is designed to be a self-administered questionnaire like Part IB, but can be reviewed by the Investigator to ensure completeness and clarity.

6.2.4 Clinical Global Impression – Improvement - Hallucinations and Delusions

The CGI-I is a clinician-rated, 7-point scale that is designed to rate the improvement in the subject’s symptoms at the time of assessment, relative to the symptoms at Baseline ([Guy 1976](#)). Severity ratings should be based on the behavioral domains of clinical concern, namely hallucinations and delusions.

6.2.5 Clinical Global Impression – Severity - Hallucinations and Delusions

The CGI-S scale is a clinician-rated, 7-point scale that is designed to rate the severity of the subject’s neuropsychiatric symptoms at the time of assessment using the Investigator’s judgment and past experience with subjects who have the same disorder ([Guy 1976](#)).

Severity ratings should be based on the behavioral domains of clinical concern, namely hallucinations and delusions.

6.2.6 Patient Global Impression of Improvement - Hallucinations and Delusions

The PGI-I is a global index used to rate the response of a condition to a therapy. It is a simple, direct, easy to use scale that is intuitively understandable to subjects and clinicians. The PGI-I asks the patient to rate their symptoms now, as compared with how it was at Baseline before beginning treatment, ranging from 1=very much better to 7=very much worse. Severity ratings should be based on the behavioral domains of clinical concern, namely hallucinations and delusions.

6.2.7 Virtual Reality Functional Capacity Assessment Tool

The VRFCAT is a tablet-based assessment that simulates key instrumental activities of daily living (iADLs) in a realistic and interactive virtual environment. With demonstrated sensitivity to basic functional capacity deficits, the VRFCAT was developed to improve clinical trials by detecting functionally meaningful improvements in patients' everyday lives ([Ruse et al. 2014](#)). The brief (VRFCAT shortened-list) version will be utilized for this study.

6.2.8 Caregiver Strain Index

The Caregiver Strain Index (CSI) is a tool that can be used to quickly identify families with potential caregiving concerns. It is a 13-question tool that measures strain related to care provision. There is at least one item for each of the following major domains: Employment, Financial, Physical, Social and Time. Positive responses to seven or more items on the index indicate a greater level of strain. This instrument can be used to assess individuals of any age who have assumed the role of caregiver for an older adult ([Robinson 1983](#); [Pearlin et al. 1990](#)).

6.2.9 Neuropsychiatric Inventory – Questionnaire Nighttime Behavior Domain

The NPI-Q was developed and cross-validated with the standard NPI to provide a brief assessment of neuropsychiatric symptomatology ([Kaufer et al. 2000](#)). The NPI-Q is a self-administered questionnaire completed by informants about patients for whom they care. Of the 12 domains in the full questionnaire, only the Nighttime Behavior domain will be completed by informants in this study.

6.2.10 Geriatric Depression Scale (Short Form)

The Geriatric Depression Scale (GDS) (Short Form) may be used with healthy, medically ill and mild to moderately cognitively impaired older adults. It has been extensively used in community, acute care, and long-term care settings. The GDS was found to have a 92% sensitivity and an 89% specificity when evaluated against diagnostic criteria. The validity and

reliability of the tool have been supported through both clinical practice and research. In a validation study comparing the Long and Short Forms of the GDS for self-rating of symptoms of depression, both were successful in differentiating depressed from non-depressed adults with a high correlation ($r = 0.84$, $p < 0.001$) ([Sheikh and Yesavage 1986](#); [Yesavage et al. 1983](#); [Stanford/VA/NIA Aging Clinical Resource Center, 2019](#)).

6.3 Safety Assessments

6.3.1 Columbia-Suicide Severity Rating Scale

The C-SSRS monitors changes in suicidal thinking and behavior over time, in order to determine risk ([Posner et al. 2011](#)). The following four constructs are measured: the severity of ideation, the intensity of ideation, behavior, and lethality.

The C-SSRS will be used to assess suicidal ideations and behaviors. The Baseline/Screening version will be administered at Visit 1 (Screening), and the “Since Last Visit” version will be administered at all other designated visits. The C-SSRS results for each subject should be reviewed by the Investigator at each visit. If at any time the C-SSRS results for a given subject reveal potential suicidality, then the Investigator should assess the clinical significance of such results. If a clinically significant risk of suicidality is identified for a subject, then the Investigator should discontinue the subject and implement appropriate treatment ([Section 4.4](#)).

This assessment is to be completed at all clinic visits.

6.3.2 Physical Examinations

A physical examination including neurological exam (cranial nerves, motor, sensory, reflexes, gait, and coordination) will be conducted.

6.3.3 Vital Signs

Vital signs will include body temperature, resting respiration rate, sitting or supine systolic and diastolic blood pressure, and pulse rate. Blood pressure should be measured after the subject has been sitting or supine for ≥ 3 minutes.

6.3.4 Height, Weight, and Body Mass Index

Height and weight will be measured and reported.

Body mass index will be calculated using the following formula:

$$\text{Weight (kg)} / [\text{height (m)}]^2.$$

6.3.5 Electrocardiograms

All 12-lead ECGs will be complete, standardized recordings. All ECGs will be centrally read; the interpretation by the central cardiologist is considered the official interpretation. Each ECG will be recorded continuously for 5 minutes.

The five minutes of ECG data will be converted into a Summary ECG (simulated 10-second ECG) for each subject. The summary ECG is created by first calculating a median beat for each lead based on all normal, good-quality beats in the lead, using standard methods and then linked together with an intervening RR interval equal to the average for the entire record. The full ECG will be evaluated algorithmically and over-read by a cardiologist. The over-reading cardiologist will review the entire 5-minute recording for arrhythmias and, if present, will add them to the interpretation of the summary ECG.

The following conditions apply:

- If the QTcF value from the ECG done at Screening is prolonged due to an identifiable cause, and it is medically appropriate to address that cause, a repeat ECG may be performed during Screening at the discretion of the Medical Monitor. In this case, the repeat ECG will be used in determination of subject eligibility.
- At Baseline, a subject may be enrolled based on the machine read of the locally completed ECG. If the interpretation of the ECG by the central cardiologist indicates QTcF outside of the allowable range, the subject will be discontinued from the study, but enrollment of the subject will not be considered a protocol deviation.

The subject must rest in a supine position for at least 3 minutes before the ECG is obtained. ECG tracings (paper or electronic) will be reviewed and interpreted by a qualified clinician. ECG tracings and results (ventricular rate, PR, QRS, QT, QTcF and QTcB intervals) will be included and summarized in the subject's study records.

6.3.6 Laboratory Evaluations

Clinical laboratory sample collection (including HbA_{1c} at Screening only) is encouraged, but not required to be completed under fasting conditions. The laboratory evaluations will include, but are not limited to, the following:

- Clinical chemistry serum tests
 - Sodium (Na), potassium (K), chloride (Cl), phosphorus (P), calcium (Ca), magnesium (Mg), carbon dioxide (CO₂), blood urea nitrogen (BUN), creatinine (CR), uric acid
 - Mg should only be performed at Visit 1 (Screening)

- Alanine aminotransferase (ALT), aspartate aminotransferase (AST), gamma-glutamyl transpeptidase (GGT), alkaline phosphatase (ALP), total bilirubin (TBIL), lactate dehydrogenase (LDH)
- Vitamin B12
 - Vitamin B12 should only be performed at Visit 1 (Screening)
- Glycosylated hemoglobin (HbA_{1c})
 - HbA_{1c} should only be performed at Visit 1 (Screening)
- Glucose
- Albumin (ALB), total protein
- Thyroid stimulating hormone (TSH) and free T4, if TSH is out of range
 - TSH/free T4 should only be performed at Visit 1 (Screening)
- Creatine kinase (CK)/creatine phosphokinase (CPK)
- Lipid panel
 - Total cholesterol, high-density lipoprotein (HDL)-cholesterol, triglycerides, low-density lipoprotein (LDL)-cholesterol, cholesterol/HDL ratio, non-HDL cholesterol
- Pregnancy test
 - A serum pregnancy test should only be performed at Visit 1 ([Table 6–1](#)) for women of childbearing potential
 - A urine pregnancy test should be performed at Baseline and all subsequent visits (except Visit 3) up to and including EOT ([Table 6–1](#)) for women of child-bearing potential
 - If urine cannot be obtained in women of childbearing potential, a serum pregnancy test should be done in its place
- Hematology tests
 - Complete blood count (CBC) including:
 - White blood cell (WBC) count
 - Complete differential (relative and absolute)
 - Hematocrit (Hct), hemoglobin, red blood cells (RBC), platelets
 - Reticulocyte count

- Urinalysis
 - Blood, RBCs, WBCs, protein, glucose, ketones, specific gravity, pH
 - Reasonable efforts should be made to collect a urine sample from all subjects. Where collection of a urine sample proves impractical or impossible (e.g., because the subject is incontinent), failure to collect a urine sample should be recorded in the subject's CRF, and will not be considered a protocol deviation.
- Urine toxicity screen
 - Urine toxicity screen will test for controlled substances at screening. The following controlled substances may be tested with a urine toxicity screen according to the schedule presented in [Table 6–1](#): amphetamine, barbiturates, benzodiazepines, cocaine, methadone, morphine/opiates, methamphetamine, marijuana (THC), phencyclidine (PCP), ecstasy (3,4-methylenedioxy-methamphetamine [MDMA]). Negative drug screens are required for study eligibility.
 - Subjects who test positive and have a valid prescription for a controlled substance may be retested if they agree to abstain from the medication for the length of their participation in the study. The repeat test, and any other tests, must be negative for them to participate in the study.

Laboratory evaluations will be completed according to the schedule presented in Table 6–1 and procedures detailed in the study laboratory manual. Additional safety testing may be performed at the discretion of the Investigator or designee.

Table 6–1 Safety Laboratory Evaluations

Visit	Tests
Visit 1 (Screening)	CHEM, CBC, UA, urine toxicity screen, serum pregnancy test
Visit 2 (Baseline)	CHEM, CBC, UA, urine pregnancy test
Visit 4 (4 weeks)	CHEM, CBC, UA, urine pregnancy test
Visit 5 (8 weeks)	Urine pregnancy test
Visit 6 (12 weeks)	Urine pregnancy test
Visit 7 (ET/EOT)	CHEM, CBC, UA, urine pregnancy test

Abbreviations: CBC=complete blood count; CHEM=clinical chemistry serum tests; EOT=end of treatment; ET=early termination; UA=urinalysis

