3.1.1 Screening Period (3-35 Days)

During the screening period, subjects will be assessed for study eligibility and prohibited medications will be discontinued if medically appropriate. Subject eligibility will be assessed by the site and the Sponsor through an eligibility review process.

Investigators should not withdraw a subject's prohibited medication for the purpose of enrolling them into the study. Medications should only be discontinued if it is deemed clinically appropriate to do so and in consultation with the treating physician.

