Anticonvulsant and mood stabilizers	PROHIBITED 
 carbamazepine lamotrigine lithium phenytoin 	
 Must be washed out 5 half-lives prior to Baseline Prohibited throughout the study until completion of the EOT visit
	RESTRICTED 
 valproate 	Valproate may be used if dose unchanged for at least 4 weeks prior to Baseline and dose is expected to remain unchanged until completion of the EOT visit.
Antidepressants	PROHIBITED 
 mirtazapine nefazadone fluvoxamine mianserin trazodone amitriptyline nortriptyline imipramine trimipramine desipramine clomipramine esketamine ketamine 	
 Prohibited throughout the study until completion of the EOT visit Must be discontinued at least 2 weeks or 5 half-lives (whichever is longer) prior to the Baseline visit
	RESTRICTED 
 citalopram escitalopram venlafaxine 	
 If subject is remaining on these medications, the dose of the permitted antidepressants on the left must be unchanged for at least 4 weeks prior to Baseline and is expected to remain unchanged until completion of the EOT visit. If the medication is being discontinued, it must be discontinued at least 2 weeks or 5 half-lives (whichever is longer) prior to the Baseline visit. 
 Citalopram is restricted to a maximum dose of 20 mg/day. Escitalopram is restricted to a maximum dose of 10 mg/day. Venlafaxine is restricted to a maximum dose of 225 mg/day
Anxiolytics	PROHIBITED 
 chlordiazepoxide diazepam flurazepam 	Prohibited at Baseline and throughout the study until completion of the EOT visit

Medication Class	Medication ^a	Prohibition/restrictions
	RESTRICTED 
 alprazolam clonazepam lorazepam oxazepam temazepam midazolam triazolam 	
 Short- or medium-acting benzodiazepine may be used for acute anxiety. Reasonable efforts should be made to use minimum dose necessary for symptom management. May not be used within 12 hours prior to an assessment visit
Hypnotics and sleeping agents	PROHIBITED 
 zolpidem zopiclone eszopiclone 	Prohibited at Baseline and throughout the study until completion of the EOT visit

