	RESTRICTED 
 zaleplon ramelteon 	May not be used within approximately 12 hours prior to an assessment (including assessments on handheld device and in clinic), and efforts should be made to limit agents to lowest dose for the shortest time needed.
Stimulants and wake-promoting agents	PROHIBITED 
 methylphenidate modafinil armodafinil 	Prohibited at Baseline and throughout the study until completion of the EOT visit (see Section 6.3.6 for procedures related to a positive amphetamine test at study entry)
Non-stimulant ADHD medications	PROHIBITED 
 atomoxetine 	Prohibited at Baseline and throughout the study until completion of the EOT visit
Serotonin antagonists	PROHIBITED 
 ciproheptadine 	
 Prohibited throughout the study until completion of the EOT visit Must be discontinued at least 3 weeks prior to the Baseline visit
Antiarrhythmic drugs	PROHIBITED 
 ajmaline amakalant, semantilide amiodarone bretlyium disopyramide dofetilide dronedarone flecainide ibutilide procainamide 	Prohibited at Baseline and throughout the study until completion of the EOT visit

Medication Class	Medication ^a	Prohibition/restrictions
	
 propafenone quinidine sotalol, d-sotalol 	
Opioids	PROHIBITED 
 methadone 	Prohibited at Baseline and throughout the study until completion of the EOT visit
Antimicrobials, antifungals, and antimalarials	PROHIBITED 
 clarithromycin erythromycin levofloxacin moxifloxacin pentamidine roxithromycin 	Prohibited at Baseline and throughout the study until completion of the EOT visit

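### Protocol Section 6.3.6 lets a subject stop a prescribed controlled medicine to pass a repeat drug screen, without the conditions that Section 3.1.1 sets for stopping medication; the passages need reconciling

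*Protocol*

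**What the plan says.** **The retest route.** Protocol Section 6.3.6 (urine toxicity screen) requires a negative screen for eligibility. A subject who tests positive and has a valid prescription "may be retested if they agree to abstain from the medication for the length of their participation in the study". It then adds: "The repeat test, and any other tests, must be negative for them to participate in the study". Neither clinical appropriateness nor the treating physician is mentioned, and there is no cross-reference to Section 3.1.1.

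**The rule on stopping medication.** Section 3.1.1 states: "Investigators should not withdraw a subject's prohibited medication for the purpose of enrolling them into the study". It continues: "Medications should only be discontinued if it is deemed clinically appropriate to do so and in consultation with the treating physician". The synopsis (Study Design) carries the same rule. Section 4.6.2.1 sets similar conditions for adjusting restricted medicines and asks that permitted ones stay at a stable dose.

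**The medication tables.** Appendix A prohibits methadone, three named benzodiazepines (chlordiazepoxide, diazepam, flurazepam) and stimulants. The stimulant row points sites to the retest text: "see Section 6.3.6 for procedures related to a positive amphetamine test at study entry". Other benzodiazepines, such as lorazepam and clonazepam, are restricted rather than prohibited: "Short- or medium-acting benzodiazepine may be used for acute anxiety".

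**The exclusion criterion.** Exclusion 20 (Section 4.2) does not list benzodiazepines among the excluding screen results. It says that as-needed use of benzodiazepines, THC or opiates need not exclude a subject once substance use disorder has been ruled out in discussion with the medical monitor.

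**The concern.** Section 6.3.6 ties abstention to being allowed into the study, and the subject's agreement is the only condition it states for the stop. A site that follows it alone could do what Section 3.1.1 tells investigators not to do. Another site, reading 3.1.1 first, could refuse the retest. The same subject might also be asked to give up a benzodiazepine that Appendix A would allow after enrolment.

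Two things are at stake. The first is protection of subjects: whether prescribed treatment may be stopped in order to enter a trial should not depend on which section a site reads. The second is interpretation. There is no control arm, efficacy is change from Baseline, and a medicine stopped just before Baseline may affect the Baseline value or the early adverse events.

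**Working it through.** The point rests on the text, not on a stated figure, so the check sets the passages side by side.

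**1. Do the two rules reach the same medicines?** The 6.3.6 panel may include benzodiazepines, methadone, barbiturates, opiates and amphetamine. Methadone and three benzodiazepines are prohibited by name in Appendix A. The prohibited stimulant row refers to 6.3.6 explicitly. So the retest route applies to medicines covered by the 3.1.1 rule.

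**2. A prohibited medicine.** Take a subject on prescribed methadone whose treating physician has no reason to stop it.
- Under 6.3.6 alone, the subject agrees to abstain, retests negative and may enter.
- Under 3.1.1, the medicine should not be withdrawn in order to enrol, and the two conditions for stopping are not met.

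The outcomes differ.

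**3. A restricted medicine.** Take a subject using prescribed lorazepam as needed.
- Under exclusion 20, a positive result need not exclude, subject to the medical monitor discussion.
- Under Appendix A, use for acute anxiety is allowed on study, within limits.
- Under 6.3.6, a negative screen is required, so the subject must abstain throughout and retest.
- Under 4.6.2.1, a restricted medicine is adjusted only if clinically appropriate and with the treating physician consulted.

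Again the outcome depends on the section followed.

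**4. Where both rules are met.** If the stop is clinically appropriate and the treating physician has been consulted, a later retest satisfies both sections. The conflict is confined to stops that do not meet the 3.1.1 conditions.

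**5. The route to the analysis.**
- Baseline is the last non-missing value before first dose (Protocol 9.5). The first dose is on the morning after the Baseline visit, and screening may last only 3 days.
- For methadone, stimulants and the prohibited benzodiazepines, Appendix A says only "Prohibited at Baseline and throughout the study until completion of the EOT visit". It states no washout interval.
- The mFSQ Psychological Function items ask about nervousness, calm and low mood (SAP 5.2.4). That subscale is one of five equally weighted parts of the primary score.
- An adverse event starting after first dose, up to 30 days after the last, is treatment-emergent (Protocol 9.5.4.1). Significant sustained worsening can define a start date (7.2.2.1), and an unclear onset defaults to treatment-emergent (SAP 5.4.3).

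**6. Can the effect be sized?** If *k* of the 53 planned subjects entered this way, each with a temporary Baseline decrement of *d* points on the mFSQ total, the mean change would shift by *k* × *d* / 53. The documents give neither *k* nor *d*. If either is zero the shift is zero, so no figure follows from the plan.

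**The case against.** The strongest reply is that the sections can be read together. Section 3.1.1 is not a flat ban: it opens by planning for prohibited medicines to be stopped in screening where medically appropriate. Its last sentence speaks of medications generally, so it can be taken to govern any stop before a retest. Section 6.3.6 permits a retest; it directs no one to withdraw anything. Section 12.3 requires consent before prohibited medicines are discontinued, and 3.1.1 adds sponsor review of eligibility. All of this stands, and it narrows the point to missing linkage. It does not remove it, because 6.3.6 reads as a complete procedure with its own condition, and Appendix A sends sites there.

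Some stronger readings are tempting but not supported:

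- *That Baseline and early adverse events are distorted.* The documents describe no withdrawal effects and no frequency of use of this route. Adverse events are recorded from consent (7.3), so one that starts before dosing and does not worsen is not treatment-emergent. Causality assessment considers concomitant medicines and pre-existing risk factors (7.2.2). Medicines are recorded from screening (4.6), so affected subjects could be identified.
- *That the shift is about a point on the mFSQ.* Assuming five subjects and 10 points each gives 5 × 10 / 53 = 0.94. Through Psychological Function alone, 10 points on the total needs a 50-point fall on that subscale (50 / 5 = 10). A 10-point subscale fall gives 5 × 2 / 53 = 0.19. All these inputs are assumed.
- *That no panel medicine has a stopping interval.* Appendix B lists phenobarbital as a strong CYP3A4 inducer, to be stopped 30 days or 5 half-lives before dosing, whichever is longer.
- *That an MMSE as low as 19 makes the subject's agreement unreliable.* Inclusion criteria 2 and 15 require understanding of the study and clear sensorium.

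**Conclusion.** The inconsistency is real as written. Section 6.3.6 makes entry depend on abstaining from a validly prescribed medicine without stating the conditions in 3.1.1, and Appendix A applies that route to a prohibited class. For benzodiazepines, 6.3.6 also disagrees with exclusion 20 and with the restricted list in Appendix A. Sites could act differently with the same subject.

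The consequence for the analysis is only a possibility. It rests on the single-arm change-from-Baseline design and on the absence of a stated washout for methadone, stimulants and the prohibited benzodiazepines. It also assumes that some subjects use the route and that stopping affects their scores or symptoms. The documents support neither assumption with a number. The effect could be near zero, and no magnitude is claimed.

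**What to change.** Reconcile Section 6.3.6 with Section 3.1.1 (and the synopsis), Section 4.6.2.1, exclusion 20 and Appendix A, in the next amendment or a clarification letter. After the change, 6.3.6 should state whether the 3.1.1 conditions govern any stop that precedes a retest. It should also agree with exclusion 20 and Appendix A on benzodiazepines. SAP Section 13.2.4 repeats the negative-screen requirement and should follow whatever is decided. Which clinical rule applies is for the sponsor.

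The cost is about a sentence in 6.3.6 with matching cross-references. The downside is small: a few subjects may not reach the retest.
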